3.6 Endpoints

Primary endpoint

The proportion of antimicrobial prescriptions adherent with prescribing guidelines delivered by mobile phone app versus paper-based prescribing guidelines at month 16 (12 months' exposure in each group)

Secondary endpoints

1. Total antimicrobial defined daily doses (DDDs) prescribed in mobile phone app versus paper-based groups of 12 months' exposure in each group

2. Proportion of patients prescribed antimicrobials by the intravenous route in mobile phone app versus paper-based groups of 12 months' exposure in each group
3. AMS knowledge level of prescribers prescribed in mobile phone app versus paper-based groups of 12 months' exposure in each group
4. Prescriber satisfaction/acceptability of the prescribing guidelines in mobile phone app versus paper-based groups of 4 months' exposure in each group
5. Total costs of antimicrobial prescribed in mobile phone app versus paper-based groups of 12 months' exposure in each group
6. Proportion of patients admitted to hospital receiving an antimicrobial prescription before and after introduction of the paper-based prescribing guidelines; and the mobile phone app prescribing guidelines + AMS training of 12 months' exposure in each group

Definitions of adherence to the guidelines

1. Full adherence with the guidelines = using correct antimicrobial agent (s) and correct dose based on the provided antimicrobial prescribing guidelines
2. Partial adherence with the guidelines = using correct antimicrobial agent (s) with incorrect dose based on provided antimicrobial prescribing guidelines
3. Non-adherence with the guidelines = using a different antimicrobial agent (s) compared to that suggested in provided antimicrobial prescribing guidelines

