measured cross-sectionally at month 0, 4, 8, 12 until month 16 after introduction of prescribing guidelines by mobile phone application versus paper-based (30). The model will compare all wedges in the intervention from month 4 to month 16 with all wedges in the reference arm from month 0 to month 12. The duration of exposure of each hospital to the reference or intervention arm will be included in the model as interaction term with the study arm in order to assess whether the duration of exposure is the effect modifier. The model will consider the correlation among the outcome's measurements from the same hospital (cluster) by adjusting for clustering in the model. Odds ratios and the corresponding confidence intervals will be obtained and reported. Tests of significance will be performed at 5% level. Analyses will be done using Stata 15.0 or higher. Likert scale analysis will be used to evaluate prescriber satisfaction with/ acceptability of paper-based compared to mobile phone app delivered antimicrobial prescribing guidelines. The satisfaction/acceptability scale will be assigned in six categories, including strongly agree=5, agree=4, neutral=3, disagree=2 and strongly disagree=1, no opinion/not use=0. Mann-Whitney test will be used to assess the differences between paper-based population and mobile phone app population. AMS knowledge level of prescribers will be assessed using questionnaires based on information in the prescribing guidelines. The overall proportion of correct answers in each time point will be compared (baseline, after paper-based guidelines (before AMS training and introduction of mobile phone app guidelines) and after AMS training and introduction of mobile phone app guidelines). Other factors such as extra AMR training program from hospital/MoH/other organizations, level of education and specialties of prescribers will also be taken into account.

Cost of antibiotic therapy will be calculated from the start date of treatment to the survey day. The unit costs for the antibiotics will be obtained from the [International Medical Product Price Guide](#).

Antibiotic defined daily dose (DDD) will be calculated using data (antibiotic agent, start date, dose and DDD of each antibiotic from www.whooc.no) from PPS in both IPD and OPD. Antimicrobial cost data from participating hospitals will also be collected each hospital pharmacy for comparison with international cost.

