5. Do you have any antimicrobial prescribing guideline App installed on your smart phone?

Yes No; If answer is "No", you do not have to answer question 6

6. How often do you access any antimicrobial prescribing mobile phone App?

Daily Nearly every day Weekly Monthly Never

A10. Prescriber feedback survey on paper-based prescribing guidelines

Prescriber feedback survey on paper-based prescribing guidelines

Date: ___/___/____, Year of graduation from medical school: _____, Speciality: _____

Department: _____ Hospital: _____

1. Have you ever seen these paper-based antimicrobial prescribing guidelines?

Yes No ; If answer is “No”, you do not have to continue this survey

2. If yes, have you ever used it?

Yes No ; If answer is “No”, you do not have to continue this survey

If the answer is “Yes”, please continue the survey

3. Complete this table below: **Instruction**-please indicate your level of agreement with the statement listed below (by ticking the box:

	Strongly agree	Agree	Neutral	Disagree	Strongly disagree	No opinion
The name of the guidelines is appropriate						
The structure is well-organised and easy to follow						
The topics covered are relevant to my patient population						
I can find information which I look for in the guidelines easily						
Language used in the guidelines is easy to understand						
Prescribing instructions (antibiotic of choice, dose and duration) are easy to follow						
The recommended antibiotics are mostly available in my hospital						
I find these guidelines restrict my choice of antibiotics						
Extra information (data on antibiotic susceptibility pattern, causes of infections in Laos, international recommendation) is useful						
Extra information (data on antibiotic susceptibility pattern, causes of infections in Laos, international recommendation) is too detailed						
Prophylaxis section is useful						
I can get more information from provided references						
These paper-based guidelines are thick and difficult to carry for my routine work						
These paper-based guidelines encourage me to document the indication for antimicrobial on hospital charts						
These paper-based guidelines encourage me to document the duration for antimicrobial on hospital charts						
Antibiotic stewardship (AMS) section is useful and relevant to my work						
These paper-based guidelines have increased my knowledge of AMS						

4. How frequently do you prescribe antimicrobial (s)?

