Daily Nearly every day Weekly Monthly Never

5. How often do you access this provided paper-based prescribing guidelines?

Daily Nearly every day Weekly Monthly Never

6. How often do you access other prescribing guidelines?

- Daily Nearly every day Weekly Monthly Never

7. How would you rate these paper-based prescribing guidelines overall?

- Very good and fitting with Lao context Good but need a bit more editing
 Moderate and need more editing Not good and need to review many sections

Please give comments in the box below:

A11. Prescriber feedback survey on mobile phone app prescribing guidelines

Prescriber feedback survey on mobile phone app prescribing guidelines

Date: ___/___/____, Year of graduation from medical school: _____, Speciality: _____,
Department: _____ Hospital: _____

1. Have you ever seen this antimicrobial prescribing guideline mobile phone application?

Yes No ; If answer is “No”, you do not have to continue this survey

2. If yes, have you ever used it?

Yes No ; If answer is “No”, you do not have to continue this survey

If the answer is “Yes”, please continue the survey

3. Complete this table below: Instruction: please indicate your level of agreement with the statement listed below (by ticking the box):

	Strongly agree	Agree	Neutral	Disagree	Strongly disagree	No opinion
The structure and design are easy to follow						
I can find information which I look for more easily than from paper-based guidelines						
Language font size and colour are easy to read						
Prescribing instructions (antibiotic of choice, dose and duration) are easy to follow						
Links to extra information (data on antibiotic susceptibility pattern, causes of infections in Laos, international recommendation) are useful						
The offline mode makes it easy for me to access the guidelines anywhere						
The App guideline encourages me to document the indication for antimicrobial on hospital charts						
The App guideline encourages me to document the duration of antimicrobial on hospital charts						
The App guideline has increased my knowledge of antimicrobial stewardship (AMS)						
Antimicrobial stewardship training increased my knowledge of AMS						

4. How often do you prescribe antimicrobial (s)?

Daily Nearly every day Weekly Monthly Never

5. How often do you access paper-based prescribing guidelines?

Daily Nearly every day Weekly Monthly Never

6. Do you carry your smart phone (with this prescribing guideline App) with you at work?

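### Secondary endpoint 4: the paper and app feedback forms share only about six of their statements, three negative paper statements score as satisfaction, and the plan does not say which items are compared or how

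*Combined protocol and SAP*

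**What the plan says.** Section 3.6 lists as secondary endpoint 4: "Prescriber satisfaction/acceptability of the prescribing guidelines in mobile phone app versus paper-based groups".

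The Statistical analysis text (within section 3.7) gives the scoring: "The satisfaction/acceptability scale will be assigned in six categories, including strongly agree=5, agree=4, neutral=3, disagree=2 and strongly disagree=1, no opinion/not use=0". It gives the test: "Mann-Whitney test will be used to assess the differences between paper-based population and mobile phone app population". The general error rate is also there: "Tests of significance will be performed at 5% level". Whether the test is one- or two-sided is not stated.

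The answers come from two different forms. Appendix A10 (paper) has 17 agreement statements. Three are worded so that agreement means dissatisfaction: "I find these guidelines restrict my choice of antibiotics", "These paper-based guidelines are thick and difficult to carry for my routine work", and one saying that the extra information "is too detailed". Appendix A11 (app) has 10 statements, none negative. One of them is already a comparison with paper: "I can find information which I look for more easily than from paper-based guidelines".

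The documents do not mention reverse scoring or a common set of items, and they do not say whether items are tested singly, summed or averaged.

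**The concern.** A two-group comparison of satisfaction needs the same quantity measured in both groups. Here the forms differ in length, content and direction of wording, while the scoring rule treats all agreement alike. A prescriber who strongly agrees that the paper book is hard to carry earns 5 points of satisfaction with it.

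Two groups with the same underlying opinion could therefore differ significantly because of the forms alone. The choice between a sum, a mean and item-by-item tests is also open, and the trial is unblinded (section 3.4). The method could be settled after the answers are known, and the possible methods do not lean the same way.

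**Working it through.** **1. Matching the forms (direct count of the A10 and A11 tables).**

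| Topic | A10 (paper) | A11 (app) | Comparable? |
|---|---|---|---|
| Structure | yes | yes, adds design | near match |
| Prescribing instructions | yes | yes | match |
| Extra information useful | yes | yes, asks about links to it | near match |
| Documenting indication | yes | yes | match |
| Documenting duration | yes | yes | match |
| Increased AMS knowledge | yes | yes | match |
| Finding information | absolute | relative to paper | no |
| Language | ease of understanding | font size and colour | no |
| Offline mode; value of AMS training | – | yes | no counterpart |
| The other nine paper statements, including the three negative ones | yes | – | no counterpart |

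Six statements match. That leaves 17 − 6 = 11 paper statements and 10 − 6 = 4 app statements without a valid comparator.

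The overall ratings do not fill the gap. A10 question 7 has four options. A11 question 9 has six, and three of those build in a preference for paper.

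**2. Score arithmetic under the stated coding.** Let a prescriber answer every statement consistently at satisfaction level s. A positive statement scores s, and a negative one scores 6 − s.

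- Paper sum = 14s + 3(6 − s); paper mean = sum / 17.
- App sum = 10s; app mean = s.

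| s | Paper mean | App mean | Paper sum | App sum |
|---|---|---|---|---|
| 5 | 73/17 = 4.29 | 5.00 | 73 | 50 |
| 4 | 62/17 = 3.65 | 4.00 | 62 | 40 |
| 3 | 51/17 = 3.00 | 3.00 | 51 | 30 |
| 2 | 40/17 = 2.35 | 2.00 | 40 | 20 |
| 1 | 29/17 = 1.71 | 1.00 | 29 | 10 |

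The maximum possible sums are 17 × 5 = 85 and 10 × 5 = 50.

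**3. Effect on the test (illustrative).** The plan gives no sample size or expected score for this endpoint, so there is no figure to reproduce. Assumptions not in the documents: equal true satisfaction on both forms, between-person SD 0.6, item SD 0.7, answers rounded to 1–5, independent respondents, a two-sided 5% test on each respondent's mean, 400 runs per setting. Group sizes run from 50 to 426 per form. The upper figure is the sum of physicians listed in section 3.2: 222 + 30 + 66 + 18 + 60 + 30.

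| Assumed mean satisfaction | False positives, all items as scored | Form favoured |
|---|---|---|
| 4.0 | 91% (n = 50) to 100% | app |
| 3.5 | 38% (n = 50) to 100% (n = 426) | app |
| 3.0 | 4% to 8% | neither |
| 2.0 | 90% (n = 50) to 100% | paper |

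Over the same settings, reverse-scoring the three negative statements gives 2.5% to 7%, and using only six matched items gives 2.8% to 7.5%. Both are nominal within simulation error.

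**4. The zero code.** Scoring no opinion as 0 ranks it below strong disagreement. Nine answers of agree and one of no opinion on the app form average (9 × 4 + 0)/10 = 3.6, not 4.0.

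This also affects a six-item mean. Assume equal satisfaction (mean 3.8, item SD 0.8) and 100 respondents per form. No-opinion rates of 5% on one form and 10% on the other then give about 40% false positives, and 5% against 15% gives over 90%. With those answers set to missing, the rate is about 5%. These no-opinion rates are assumptions.

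**The case against.** The strongest reply is that the plan never says items are combined. Item-by-item testing is an equally open reading, and under it the three negative statements have no app counterpart and never enter a comparison. That stands: the scoring bias is conditional on an all-item score. It does not make the plan adequate, because item-by-item testing is valid only for the matched statements, which the plan does not select.

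The forms also differ partly on purpose. Section 3.5 says the app carries the same content as the paper version, so asking again about topics or prophylaxis would add little. Section 3.7 gives the app survey the aim of learning how prescribers find the app compared with paper. Unequal forms are not an error in themselves; the gap is in the analysis that compares them.

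The simulation assumes that each negative statement mirrors overall satisfaction. A prescriber may value the content and still find the book thick, so the rates are illustrative.

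A reader might infer that any overall score favours the app. The arithmetic does not support this. A sum favours paper, and a mean favours the app only when prescribers are satisfied.

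**Conclusion.** The point holds as a defect in the scoring and specification of a secondary endpoint. The stated coding gives the wrong sign to three paper statements, and neither an all-item mean nor an all-item sum is comparable between the forms. The counts and score arithmetic need no outside assumption beyond a prescriber who answers consistently.

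The false-positive rates do need assumptions. On an all-item mean they run from about 5% near neutral to 90% or more when prescribers are clearly satisfied or dissatisfied, and no single figure within that range can be taken from the documents. It would also go too far to say that the planned comparison is certainly biased, since the plan does not commit to an all-item score. The primary adherence analysis is untouched.

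**What to change.** Amend the Statistical analysis text before the answers are examined:

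- Define the endpoint 4 comparison as the six matched statements, listing them and noting that structure and extra information are near matches. State in advance whether they are tested item by item or as their mean.
- Reverse-score the three negative A10 statements (6 minus the score) in any paper total.
- Treat no opinion or no use as missing, and report its frequency by form instead of scoring it 0.
- Report the remaining 11 paper and 4 app statements descriptively, by form.

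This changes wording only and needs no new form, visit or data. The cost is that the unmatched statements become descriptive.
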